This hypothesis will be tested by implementing a novel model of repeated exposure to experimentally-induced insomnia symptoms, consisting of 3 consecutive 4-day episodes, each starting with 3 nights of sleep characterized by typical insomnia symptoms (delayed sleep onset, sleep disruption, early morning awakening), followed by a single recovery night of 8 hours of sleep. This model mimics sleep patterns that are typical in insomnia populations^{31;41} as well as chronic pain populations^{28;29}. Twenty-six healthy women and men will be studied in an intra-individual balanced design, with each participant undergoing 2 18-day-in-hospital conditions (total number of days include baseline and additional recovery nights), one consisting of repeated exposure to insomnia symptoms induction and the other serving as control condition with 8 hours of sleep per night. Frequent blood and urine sampling as well as administration of a complex pain testing battery will be obtained and utilized to evaluate the following aims:

Aim 1 will investigate the **inflammatory response** to repeated exposure to experimentally-induced insomnia symptoms. We postulate that there will be a progressive increase in pro-inflammatory markers (IL-6, PGE2) and decrease in anti-inflammatory lipid mediators (resolvins), leading to **sensitization of the nociceptive system**, as manifested by lower pain thresholds to pressure and heat, as well as increased temporal summation of pain (an index of central sensitization).

Aim 2 will investigate the **pain-inhibitory response** to repeated exposure to experimentally-induced insomnia symptoms. We postulate that there will be a progressive deterioration in the capability to inhibit pain (measured by the conditioned pain modulation test, resulting in **less habituation to pain** (as measured by pain intensity ratings to daily pain supra-threshold stimuli).

Aim 3 will investigate the **ability of the inflammatory and pain-inhibitory system to recover** from the effects of experimentally-induced insomnia symptoms. We postulate a progressive impairment of systems to return to baseline upon repeated exposure to insomnia symptoms.

B2. SIGNIFICANCE AND BACKGROUND FOR THE STUDY

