Recovery from deficient sleep has been rarely studied, but we and others have shown that after a single episode of sleep restriction or total sleep deprivation, the inflammatory marker IL-6 (plasma and mRNA levels) do not normalize after one night or even two nights of recovery sleep⁴². Furthermore, preliminary data from our ongoing study suggest that the expression of IL-6 by monocytes never fully returns to baseline during brief recovery sleep periods occurring during a longer period of sleep restriction (see **Figure 3**). From this perspective, (and as depicted in **Figure 2**), we expect that during a single night of recovery sleep (typical for insomnia^{31;41}) between successive episodes of experimental insomnia, the ability of inflammatory systems markers to return to baseline will progressively decline, and their sensitizing actions will prevent normalization of pain measures (i.e., pain thresholds and temporal summation of pain). Similarly, we assume that recovery of the pain-inhibitory system will not be fully achieved during a single night of good sleep in-between experimental insomnia episodes, leading to a situation where the next exposure to insomnia ‘hits’ an incompletely recovered system. As depicted in **Figure 2**, we expect that the ability of the pain-inhibitory system to return to baseline will progressively decline during successive recovery sleep periods, leading to less habituation to pain over time, as manifested in a failure to experience supra-threshold pain as less intensive across day-to-day exposure.

Summarizing the importance and implications of the knowledge gained:

- (1) While it has long been known that insomnia is highly comorbid with chronic pain conditions, we still do not have a good understanding of the underlying mechanisms. To our knowledge, this proposal will be the first to investigate the mechanistic roles of two processes that we hypothesize to underlie insomnia-induced pain processing abnormalities: (a) Inflammatory-induced sensitization of the nociceptive system and (b) pain-inhibitory-induced habituation.
- (2) Considering the high life-time prevalence of insomnia and chronic pain, as well as their high comorbidity, mechanistic knowledge is essential for the development of specific targets to prevent or ameliorate pain amplification due to insomnia. As it is unlikely that we will eradicate insomnia in

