Outcome variables will be measured on 8 out of the 18 in-hospital protocols (baseline, 2nd experimental insomnia/control night and 4th recovery night of each episode, and 3rd recovery night at end of protocol). The analysis will focus on episode-wise comparison of outcome variables between experimental insomnia and control sleep conditions. Although several forms of linear mixed model will be used, our main analysis will focus on daily summary measures (mean, max, min, slope, AUC, etc.) The models will be constructed as follows: the study has two within factors (measurements over several days and measurements within the same day). Data will be used as it is or the difference between the two experimental conditions by episode will be used in the analysis. The main method of data analysis will employ linear mixed model (repeated measures analysis).

By defining appropriate contrast we can evaluate (i) the difference between experimental insomnia nights and recovery sleep nights for the entire study period, (ii) the difference between days 3 and 6 (day6 minus day3), 7 and 10, and 11 and 14 separately. We expect that each of the contrasts will yield a significantly positive value. These comparisons will show if IL-6 values drops or increases from experimental insomnia nights to recovery sleep nights. Similarly, from the same model, by defining appropriate contrasts, we will evaluate the difference between days 6 and 7, 10 and 11, and 14. These contrasts are expected to be negative. Time will also be used as a continuous variable to test the trend and quadratic effect, and if the above contrast does not suggest strong episode-wise effect but mild increment (or decrease) from one episode to the next. We may also use piece-wise regression with a knot at each episode (and also with just one knot to capture the effect of prolonged recovery towards the end of the experiment). As mentioned earlier, many of the exploratory analysis will be guided by plots and summary assessment of the data. Other inflammatory marker (PEG2, resolvins) will be analyzed in a similar fashion.

Sensitization variables (HPT, PPT, TS) will be analyzed similarly and are expected to mimic the time course of inflammatory variables. Correlation between inflammatory markers and sensitization variables will be evaluating using the Altman-Bland method². The linear mixed model described above can be used to obtain the necessary estimates to compute this correlation.

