Assessment of Aim 2: Pain-inhibitory response and its relation to indicators of habituation to pain upon repeated episodes of experimentally-induced insomnia symptoms. Analysis will follow the strategy similar to one outlined in Aim 1. To evaluate co-variation of the pain-inhibitory response with indicators of habituation we will first obtain average values of each value for each day, and use the Altman-Bland correlation approach described earlier.

These data will be analyzed using linear mixed model for doubly repeated measures using SAS GLM procedure as described in:

http://support.sas.com/documentation/cdl/en/statug/63033/HTML/default/viewer.htm#statug_glm_sect054.htm.

Assessment of Aim 3: Recovery of the inflammatory and pain-inhibitory response upon

repeated episodes of experimentally-induced insomnia symptoms. The proposed incomplete resolution of inflammatory and pain-inhibitory responses during the recovery nights and the progressive impairment of these responses across insomnia induction episodes will be evaluated using a mixed model approach and utilizing four time points: baseline, and recovery at the end of 1st, 2nd, and 3rd insomnia episode. Recovery response will be further evaluated by comparing effects of a single night of recovery sleep to a set of 3 nights of recovery sleep at the end of the protocol. Data analysis for this aim is similar to data analysis described for Aim 1, but a different set of contrasts need to be defined. Our conjecture is that during the recovery IL-6 drops but does not reach to the level of previous recovery. To test this we will evaluate contrasts that compare IL-6 values at days 3 and 7, 7 and 11 and 11 and 15. Finally, the difference between day 15 and 17 is assumed to be larger than any other difference between sleep restriction and recovery days. To test this we will evaluate the differences between other recovery days (average of days 7, 11, and 15) and day 17. All analysis will be performed using SAS statistical package (version 9.3).

C. Subject Selection

Human Subjects Involvement and Characteristics

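### Aim 1 sets out to compare insomnia with control sleep, but its written contrasts mostly use partly recovered nights as reference and so measure only acute within-episode change

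*Combined protocol and SAP*

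**What the plan says.** B1 states the Aim 1 hypothesis: "there will be a progressive increase in pro-inflammatory markers (IL-6, PGE2"), with a matching fall in resolvins, leading to sensitization.

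In B3, Assessment of Aim 1, the declared emphasis is the comparison of the two sleep conditions episode by episode. The values analysed may be raw or insomnia-minus-control differences; the choice is left open. The contrasts then written out are:

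- contrast (i), a single whole-stay comparison: "the difference between experimental insomnia nights and recovery sleep nights for the entire study period";
- contrasts (ii), one per episode, each taken on its own: day 6 less day 3, day 10 less day 7, day 14 less day 11.

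Of these the plan says: "We expect that each of the contrasts will yield a significantly positive value". Day 3 is baseline, days 6, 10 and 14 follow insomnia nights, and days 7 and 11 follow recovery nights. A further set compares each insomnia day with the recovery day after it and is expected to be negative. Linear and quadratic time trends and optional piecewise regression are added. The other inflammatory markers, HPT, PPT and TS are to be analysed similarly, and Aim 2 follows the same strategy.

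On recovery, B2 reports preliminary data in which "the expression of IL-6 by monocytes never fully returns to baseline during brief recovery sleep periods". It expects that between episodes "the ability of inflammatory systems markers to return to baseline will progressively decline", and that "recovery of the pain-inhibitory system will not be fully achieved during a single night of good sleep". Assessment of Aim 3 adds: "Our conjecture is that during the recovery IL-6 drops but does not reach to the level of previous recovery". Aim 3 tests this with days 3 v 7, 7 v 11 and 11 v 15.

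**The concern.** Aim 1 asks how far the markers rise in response to repeated insomnia. A contrast that answers this needs a reference free of insomnia exposure: the same day of the control stay, or day 3. Among the contrasts written for Aim 1, only day 6 minus day 3 starts from such a point. None compares day 10 or 14 with day 3, or any insomnia day with its control day.

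The remaining contrasts use recovery days that the plan expects to carry part of the insomnia response, and that part drops out of the subtraction. Analysing insomnia-minus-control differences does not cure this, because the carried-over part sits in both days being subtracted. If raw values are used, the control stay does not enter these contrasts at all, although B3 (Study Design) says it is needed because markers have fallen during control stays in the research unit.

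At stake is interpretation as well as power. A small contrast (i) could mean a weak response or a persistent one, and equal episode contrasts could mean stability or accumulation. Table 1 is built on deficient versus control sleep, so its power figures do not transfer to contrast (i).

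**Working it through.** **1. The plan's own figures.** Table 1 uses a paired t-test, alpha 0.05, N=26 (sidedness not stated; two-sided assumed). With noncentrality (mean/SD)×√26 and 25 df:

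- IL-6 positive monocytes: 38/66 = 0.576; ×5.099 = 2.94; power 0.81.
- Plasma IL-6: 1.95/1.59 = 1.226; power >0.99.
- CPM: 47/54 = 0.870; power 0.99.

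All agree with the stated >0.80.

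**2. What the contrasts estimate.** Take insomnia-minus-control levels, with each episode adding one unit to whatever was carried over. Contrast (i) is the mean of days 6, 10, 14 minus the mean of days 7, 11, 15 (day sets inferred from contrasts (ii) and Aim 3).

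| Pattern | Days 3, 6, 7, 10, 11, 14, 15 | (i) | (ii) | Mean insomnia v control | Day 14 minus day 6 |
|---|---|---|---|---|---|
| Full recovery | 0, 1, 0, 1, 0, 1, 0 | 1.00 | 1, 1, 1 | 1.00 | 0 |
| Worsening recovery (25/50/75% persists) | 0, 1, 0.25, 1.25, 0.625, 1.625, 1.219 | 0.59 | 1, 1, 1 | 1.29 | 0.625 |
| Stepwise build-up (limiting case) | 0, 1, 1, 2, 2, 3, 3 | 0 | 1, 1, 1 | 2.00 | 2 |

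For the middle row, (i) = (1+1.25+1.625)/3 - (0.25+0.625+1.219)/3 = 1.29 - 0.70 = 0.59. Contrast (i) shrinks as the true response grows, and contrasts (ii) are identical in all three rows. If day 3 also counts as a reference night, (i) is 0.77 in the middle row and 0.50 in the last: attenuated less, but still attenuated.

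**3. Power.** Assumptions: the same-day difference has SD 66 on every day, with equal correlation rho between days; its mean is 38 on the three insomnia days and f×38 on days 7, 11 and 15. The documents give neither f nor rho.

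- Contrast (i): mean (1-f)×38, SD 66√(2(1-rho)/3).
- Same-day mean: mean 38, SD 66√((1+2rho)/3).
- Same-day mean adjusted for day 3: mean 38, SD 66√((1+2rho)/3 - rho²), 24 df.

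Example, rho=0.5 and f=0.5: SD = 66√(1/3) = 38.1; 19/38.1 = 0.499; ×5.099 = 2.54; power 69%.

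| rho | SD of (i) | (i), f=0.25 | (i), f=0.5 | (i), f=0.75 | Same-day (SD) | Day-3 adjusted (SD) |
|---|---|---|---|---|---|---|
| 0.3 | 45.1 | 87% | 54% | 18% | 97% (48.2) | 99% (43.9) |
| 0.5 | 38.1 | 96% | 69% | 23% | 93% (53.9) | 99% (42.6) |
| 0.7 | 29.5 | >99% | 88% | 35% | 88% (59.0) | >99% (36.7) |

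By the same formulas, plasma IL-6 (1.95±1.59) keeps at least 99% power in contrast (i) at f=0.5 and 60-92% at f=0.75. CPM (47±54) keeps at least 88% at f=0.5.

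**The case against.** The case for the plan has real weight.

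- **Role of contrast (i).** The plan never names it as the primary test. It says the contrasts can be evaluated, and that they show whether IL-6 moves between insomnia and recovery nights. For that acute question the reference is right. A reader might infer that the main test has the wrong null; the text does not support that.
- **Declared focus.** Insomnia versus control by episode is already the stated emphasis. This stands, and it is why the point is one of specification: the emphasis never becomes a contrast.
- **Carry-over is tested elsewhere.** Aim 3 compares successive recovery days, and Aim 1 adds time trends. A reader might infer that the persistent response is lost, or that Aims 1 and 3 defeat each other. Neither follows: Aim 3 estimates what the Aim 1 contrasts remove. But it does so on recovery days, and the trend has no stated condition term, so neither estimates the response against control on days 10 and 14.
- **Partial recovery.** It is tempting to set f=1 and say contrast (i) has only its 5% error rate. The plan expects IL-6 to drop on recovery nights and the insomnia-to-recovery contrasts to be negative. Complete persistence is not its hypothesis.
- **Small carry-over.** At f=0.25 contrast (i) is more powerful than the unadjusted same-day mean at rho 0.5 and 0.7; at f=0.5 and rho=0.7 they tie at 88%. This stands, although the adjusted comparison matches or beats it throughout that range.

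**Conclusion.** The point holds as a mismatch between the declared Aim 1 focus and the contrasts written for it. Apart from day 6 minus day 3, they measure acute within-episode change and remove what is carried over. They cannot reveal a progressive increase that comes from build-up on an incompletely recovered system; they would show one only if the acute rise itself grew by episode.

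The cost ranges from nothing at f=0, through moderate at f=0.5, to severe at f=0.75 for an effect the size of the monocyte row. It is small for plasma IL-6 until f is near 0.75.

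These sizes rest on assumed f and rho, equal SDs across days, and 66 being the SD of a same-day difference. Table 1 labels its entries as response differences; if 66 is already the SD of a change from baseline, the gain from day-3 adjustment is smaller. The direction of the attenuation needs none of these assumptions, only that some response persists on recovery days.

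**What to change.** Write the main Aim 1 contrast as the insomnia-minus-control difference on days 6, 10 and 14, adjusted for day 3. Report it as an average over the three days and as a linear trend over episodes (coefficients -1, 0, 1). Fit both stays in one model, or analyse the between-condition differences, instead of leaving that choice open. Carry the same contrast to the other inflammatory markers, HPT, PPT, TS and the Aim 2 outcomes. Keep contrast (i), day 10 minus day 7 and day 14 minus day 11, labelled as acute within-episode change. The Aim 3 contrasts can stay.

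The cost is SAP wording and different contrast coefficients in the same model, with no new data. The downside is that, if recovery is nearly complete, the same-day comparison without day-3 adjustment is somewhat less precise than contrast (i): 88% against about 100% power at rho=0.7 and f=0. Under the assumptions above, day-3 adjustment removes most of that difference.

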This study will employ an intra-individual balanced 2 x 18-day in-hospital protocol (experimental insomnia vs. control sleep condition, see **Figure 8**). The first 2 nights of each 18-day protocol will be adaptation nights, and the 3rd night will serve as the baseline night, with a sleep opportunity of 8 hours (23pm-7am) on all 3 nights. In the experimental insomnia study arm, insomnia symptoms will be induced during the next 3 nights, followed by 1 night of 8-hour recovery sleep (for more details, see model description under Procedures). During nights with insomnia symptom induction, sleep onset will be delayed by 1 hour (midnight 12am), the sleep period (12-6am) will be disrupted by hourly 20 min long awakenings, and sleep offset will be advanced by 1 hour (6am). This episode of 3 nights of experimental insomnia followed by 1 night of recovery sleep will be repeated three times. After the last experimental insomnia episode, participants will have 4 recovery nights. In the control arm of the study, participants will receive an 8-hour sleep opportunity for all 18 nights of the protocol. These 2 arms of the study will be separated by an interval of at least 1 month in order to allow recovery from blood sampling. Monthly separation was chosen to control for potential effects of menstrual phase in women. Depending on the bed occupancy space, participants will stay in a private room in the CRC. If a private room is not available, participants will stay in a double occupancy room with an individual of the same sex (assigned at birth)

Visit 1. Initial screening. All potential participants will have the study explained to them in detail by the PI or another senior member of the research team. If interested, potential participants will sign the informed consent and nursing staff in the Clinical Research Center (CRC) will take vital signs and collect a blood sample. A short battery of screening tests and questionnaires will also be collected in order to assess health status (see **Appendix 1** for blood tests and questionnaires). Potential participants will then be introduced to the web-based, secured diary recording system (REDCap²²) and given an actigraphy watch to take home to estimate sleep-wake habits, for 2 weeks (see **Appendix 1**). These data will be used to verify nightly sleep duration between 7 to 9 hours to be used for eligibility.

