Polysomnographic recording (PSG). Sleep will be recorded using the Embla system N7000 (Medcare US, Buffalo) on the screening night visit to ensure that participants are free from sleep disorders. The Embla system will also be used to collect sleep data on the 8 intensive recording days of each study run (baseline, every 2nd and 4th night of each episode, 3rd recovery night at end of protocol). The PSG montage will follow standard criteria and sleep EEG will be manually stage-scored on a 30 second epoch basis³. The main purpose for sleep data collection is the quantification and comparison of various sleep indices in insomnia symptoms induction and control nights (e.g., sleep duration, sleep latencies, percent time spend in different sleep stages). For explorative analysis (not specified in aims), spectral analyses will be conducted on EEG data using Remlogic software (Medcare US, Buffalo). The homeostatic response will be calculated for each episode, by calculating change from baseline for the two homeostatic markers N3 (slow wave sleep) and delta power, and comparing between episodes. We will explore whether the robust and stable homeostatic response that has been observed within exposure to a single episode of deficient sleep¹ will increase with episode repetition. Spectral analysis will be performed by the PI, who is experienced in this analysis¹⁹.

Blood Sampling. On the baseline day (Day 3), as well as on the 8 intensive recording days of each 18-day study run, blood samples will be drawn at 1100am and after pain testing, around 1550 (50 min after pain testing) per simple needle stick. The amount of the blood collected at each blood draw will range between 10ml and 50ml. The total amount of blood taken over each 18-day protocol will not exceed 550ml.

IL-6 will be measured in plasma in our laboratory, using a high sensitivity enzyme immunosorbent assay (ELISA, Quantikine ® HS, R&D Systems, Minneapolis, MN). We will measure IL-6 twice throughout the 8 intensive recording periods. IL-6 will be also measured in vitro as the capacity of monocytes to express IL-6. In brief, whole blood will be stimulated with lipopolysaccharide (LPS,

100pg/ml), incubated with fluorescence-conjugated antibodies (CD14, CD45, IL-6), and IL6-positive monocytes will be quantified using flow cytometry (Gallios™ Beckmann-Coulter Inc, Flow Cytometry Core at BIDMC).

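### Aim 1's day 6 minus day 3 contrast makes no use of baseline adjustment, so comparing it between insomnia and control gives up precision that the day-3 values already collected could usually recover

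*Combined protocol and SAP*

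**What the plan says.** The design (B3, Study Design) is a two-condition crossover: "This study will employ an intra-individual balanced 2 x 18-day in-hospital protocol". Within each stay "the 3rd night will serve as the baseline night", and the Blood Sampling section confirms that samples are drawn then: "On the baseline day (Day 3), as well as on the 8 intensive recording days of each 18-day study run". Every completer therefore has two day-3 values, one per stay, both obtained while the two arms are still on the same 8-hour schedule.

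For Aim 1 the stated emphasis is between conditions: "The analysis will focus on episode-wise comparison of outcome variables between experimental insomnia and control sleep conditions". The main method is a linear mixed model for repeated measures. The form of the data is left open: "Data will be used as it is or the difference between the two experimental conditions by episode will be used in the analysis". Among the contrasts that may be drawn from the model is "the difference between days 3 and 6 (day6 minus day3), 7 and 10, and 11 and 14 separately", each expected to be positive. Aim 3 uses the baseline once more: "To test this we will evaluate contrasts that compare IL-6 values at days 3 and 7, 7 and 11 and 11 and 15".

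Nowhere is the day-3 value named as a covariate, and nowhere is its mean constrained to be equal in the two conditions.

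**The concern.** Day 3 precedes any difference between the arms, so it carries no information about the effect of insomnia. Its only use in a between-condition comparison is to remove noise. Subtracting it removes noise well only when the day-3 and day-6 differences between stays are highly correlated; otherwise the subtraction adds the noise of two baseline measurements. Regression on the baseline takes out only as much of it as is predictive.

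A mixed model does not solve this by itself. If day 3 is one of the responses and its mean is free in each condition, the condition-by-day contrast for day 6 against day 3 still has the change-score variance.

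What is at stake is precision in a trial where participants are expensive: each completer spends 2 × 18 = 36 days in hospital, and about 18 people are screened for each one admitted. Precision that can be had from data already planned is worth taking.

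**Working it through.** **Inputs.** From the document: N = 26 completers, α = 0.05, paired t-test (Table 1); a day-3 baseline in each stay; the day 6 minus day 3 contrast. Not in the document, and therefore assumed over a range: r, the correlation between the day-3 and day-6 insomnia-minus-control differences, and k, the SD of the day-3 difference divided by the SD of the day-6 difference.

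**Step 1: the plan's own figure.** Reading ± in Table 1 as an SD and taking a two-sided test (neither is stated), power from the noncentral t at N = 26 is 1.000 (plasma IL-6), 0.806 (IL-6 positive monocytes; noncentrality √26 × 38/66 = 2.94), 0.989 (CPM), 0.837 (CPT habituation) and 0.987 (CPT habituation after recovery sleep). All exceed 0.80, so the table's claim reproduces.

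**Step 2: the variance ratio.** Write D3 and D6 for a participant's insomnia-minus-control difference on each day, with Var(D6) = V.

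- Change score: Var(D6 − D3) = V(1 + k² − 2kr), which is 2V(1 − r) when k = 1.
- Baseline-adjusted: V(1 − r²).
- Ratio: 1 + (k − r)²/(1 − r²), which is 2/(1 + r) when k = 1.

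**Step 3: the cost of estimating the slope.** With an intercept, a sequence term and one baseline slope at N = 26, the adjusted variance rises on average by the factor 1 + 1/(26 − 4) = 23/22 = 1.045. Dividing the ratio by this gives the net figure. A simulation of a 26-person crossover (10,000 runs, baseline difference and sequence in the model) serves as a check.

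| r (k = 1) | 2/(1+r) | after slope cost | net inflation | simulated ratio |
|---|---|---|---|---|
| 0 | 2.00 | 1.913 | 91.3% | 1.86 |
| 0.3 | 1.54 | 1.472 | 47.2% | 1.47 |
| 0.5 | 1.33 | 1.275 | 27.5% | 1.29 |
| 0.8 | 1.11 | 1.063 | 6.3% | 1.05 |

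Break-even is where 2/(1 + r) = 23/22, that is r = 44/23 − 1 = 0.91. With k = 1 and r below 0.5, 2V(1 − r) exceeds V, so subtracting the baseline is then less precise than ignoring it.

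**Step 4: unequal SDs.** Before the slope cost, k = 0.8 gives inflation of 64%, 12% and 0% at r = 0, 0.5 and 0.8; k = 1.25 gives 156%, 75% and 56%. The ratio never falls below 1, but it equals 1 when k = r.

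**Step 5: where r is likely to lie.** Stable differences between people, which make raw day-to-day correlations high, cancel in D3 and D6. Only variation specific to a stay and shared by its day 3 and day 6 contributes to r. A value near 1 should not be presumed, but the document offers nothing from which to estimate it.

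**The case against.** The strongest reply is that the plan does not make this contrast the Aim 1 response. It is offered as something the model can supply, next to a comparison of insomnia with recovery nights over the whole study, linear and quadratic trend, and piecewise regression. It may also be meant as a within-condition time course: the text goes on to speak of IL-6 moving between insomnia and recovery nights, and raw values are one of the two permitted data forms. On that reading the variance ratio does not apply. This stands as a limit. The point holds only for the version compared between conditions, as condition differences or a condition-by-day term. That version is nevertheless the one that answers the stated Aim 1 focus, and the plan itself says a control stay is needed because the hospital environment shifts the outcomes.

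The scope is also narrow. Of the three rise contrasts only the first uses day 3; days 7 and 11 come after exposure, so day 10 minus 7 and day 14 minus 11 are different quantities. In Aim 3 only day 3 versus day 7 uses the baseline, and there it addresses return to baseline directly. Replacing it with insomnia minus control at day 7 would change the question.

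A reader might infer three stronger things, none of which the document supports:

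- **That the trial loses 11% to 100%.** This is just 2/(1 + r) − 1 at r = 0.8 and r = 0 with equal SDs, before the slope cost. It is not a property of this trial.
- **That adjustment wins at every correlation below 1.** At N = 26 it does not, once the slope has to be estimated.
- **That Table 1 is wrong or the study underpowered for this reason.** The monocyte row, the tightest, describes a response to three cycles of sleep restriction rather than a day-6 contrast, and what its SD of 66 refers to is not said. If it is a change-score SD, 0.806 is already the planned power and adjustment at r = 0.5 would raise it to 0.903 (before the slope cost). If it is an adjusted SD, the change score at r = 0.5 would have 0.686. Nothing in the document decides between these.

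**Conclusion.** The point holds as a matter of efficiency. Compared between conditions, day 6 minus day 3 is a difference of change scores, and nothing in the plan adjusts for a baseline that is available in both stays. With equal SDs the variance is inflated by about 91%, 47%, 27.5% and 6% at r = 0, 0.3, 0.5 and 0.8 after the slope cost at N = 26. The inflation is nil near r = 0.9 and can be near zero for some unequal SDs. These sizes rest on assumed values of r and k. The change score is not biased in this balanced randomised crossover, no stated figure is in error, and the plan does not forbid adjustment. The change is worth making because it is specific, uses data already collected and is nearly free.

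**What to change.** In Assessment of Aim 1, state that insomnia minus control is estimated at each post-baseline recording day from the mixed model, with adjustment for day 3 in one of two ways:

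- Post-baseline days are the response. The stay's day-3 value is a covariate, split into the participant's mean of the two day-3 values and the stay's deviation from that mean. The split keeps the within-person slope, which matters for this contrast, separate from the between-person slope.
- Day 3 stays in the response, with its mean constrained to be equal in the two conditions.

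Both assume that the first stay leaves no shift in day 3 of the second; the plan should say so.

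Keep day 10 minus day 7 and day 14 minus day 11 as within-episode contrasts, and keep day 3 versus day 7 in Aim 3 as the return-to-baseline contrast. For Aim 3, the baseline-adjusted insomnia-minus-control difference at the recovery days can be reported alongside. State also whether each listed contrast is taken within a condition or between conditions.

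The cost is a change of wording and one or two degrees of freedom. If r turned out to be above about 0.9 with equal SDs, adjustment would be marginally less precise than the change score.
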